#### 9.1.5 Treatment Given as a Result of the Event

The event impact in terms of treatment provided will be as either: none, medication administered, non-medication therapy administered, surgery, or other (with a specification).

[figure not shown]
### 9.1.6 Outcome Assessment

The outcome of the event will be assessed as either: resolved, resolved with sequelae, ongoing, or death. Only one AE per subject is allowed to have an outcome assessment as "death." If there are multiple causes of death for a given subject, only the primary cause of death will have an outcome of death.

## 9.1.7 Expected / Anticipated Adverse Events

The most common potential study drug-related adverse reaction reported is mild headache. Other adverse events likely to be related to the drug include mild to moderate diarrhea, nausea, and fatigue.

CONFIDENTIAL Page 88 of 108

# 9.1.8 SC Injection-related Events

SC and IV injections of concentrated protein materials can be associated with injection-related AEs that impact the ability to safely and successfully deliver the drug. Local injection-site reactions may include pain/discomfort, induration, erythema, nodules/cysts, pruritis, ecchymosis, etc. For SC injections, bleeding, absorption of the drug, leakage of drug, and induration at the local injection site can be additional complications. Other AEs that are common to monoclonal antibody-based therapies are chills, headache, backache, malaise, fever, pruritis, rash, nausea, tingling, and hypertension.

SC Injection-site reactions thought to be directly related to the injection are considered to be AEs of special interest, and a separate guideline for the acquisition of data related to this AE of special interest is provided in section 17.1.

# 9.1.9 Stopping Rules for PRO 140

Subjects who develop Grade 1 or Grade 2 adverse events will continue per protocol. If a subject chooses to discontinue study treatment, the site should notify the protocol team leadership, and encourage the subject to complete any remaining study visits until the toxicity resolves.

For subjects who develop Grade 3 or higher adverse events per below, or experience graft failure or relapse the study treatment will be permanently discontinued:

- Grade 3 or higher liver toxicity not attributable to other causes such as infection, GVHD or Sinusoidal Obstruction Syndrome (SOS);
- Grade 3 or higher toxicity which is assessed by the investigator to be definitely, probably or possibly related to the study drug;
- Graft failure or relapse;

# 9.1.10 Study Stopping Rules

Upon occurrence of any of the following events, data will be reviewed by the Data Monitoring Committee (DMC):

- 1. Occurrence of a Grade 4 toxicity or two (2) occurrences of Grade 3 toxicities that are assessed to be definitely, probably or possibly study drug-related by the treating investigator;
- 2. Occurrence of more than 20 percent mortality by day +100;
- 3. Occurrence of more than 5 percent graft failures by day +100;
- 4. Occurrence of 5 or more of the first 10 subjects experiencing acute Grade II-IV GVHD.

CONFIDENTIAL Page 89 of 108

Version 3.0 Date: 17 Jun 2016

The DMC will make a recommendation to the study investigators, who, in consultation with the sponsor will decide whether to stop enrollment in the study.

[figure not shown]

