# 9.1.1 Reporting of Adverse Events

Report initiation for all AEs and SAEs will begin at the time of the first treatment and continue up until the final study visit (i.e. up to the Follow-up visit). All events will be followed to resolution or until 30 days after the subject completes the study. A final assessment of outcome will be made at that time.

All AEs must be recorded in the subject's medical records and on the eCRFs. AEs will be reported using customary medical terminology along with the following information: the onset and end dates, whether the event is considered to be a SAE (see section 9.2), the impact the event had on study treatment (see section 9.1.2), the CTCAE grade (intensity) of the event (see section 9.1.3), the causality of the event (see section 9.1.4), whether treatment was given as a result of the event (see section 9.1.5), and the outcome of the event (see section 9.1.6).

[figure not shown]

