## 9.1.3 CTCAE Grade (Severity) Assessment

The investigator will carefully evaluate the comments of each subject and the response to treatment in order to judge the true nature and severity of the AE. To assess severity, the

CONFIDENTIAL Page 86 of 108

investigator will use the guidelines outlined in CTCAE v4.03. The general guidelines for assessing the AE grade appear below. Full guidelines may be obtained at http://evs.nci.nih.gov/ftp1/CTCAE.

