**Table 9-1: CTCAE v4.03 General Guidelines** 

Grade	Description
Grade 1	Mild; asymptomatic or mild symptoms; clinical or diagnostic observations only; intervention not indicated.
Grade 2	Moderate; minimal, local, or noninvasive intervention indicated; limiting age- appropriate instrumental activities of daily living (ADL)*.
Grade 3	Severe or medically significant but not immediately life-threatening; hospitalization or prolongation of hospitalization indicated; disabling; limiting self care ADL†.
Grade 4	Life-threatening consequences; urgent intervention indicated.
Grade 5	Death related to AE.

\*Instrumental ADL refer to preparing meals, shopping for groceries or clothes, using the telephone, managing money, etc.

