# 12 DATA MONITORING COMMITTEE (DMC)

A Data Monitoring Committee (DMC), independent of the study operations will be established to consider safety data generated during the study and to make recommendations about IA data. The details of the DMC responsibilities will be included in the DMC charter. The DMC charter will be developed and operated in adherence to the current FDA guidance on DSMC (Establishment and Operation of Clinical Trial Data Safety Monitoring Committees [March 2006]). The DMC meetings will take place at least once after the IA, and at other time-points as determined by the DMC charter, if necessary. In addition to the pre-specified time-points, the DMC may also decide to schedule a meeting whenever they decide a review of emergent safety data is warranted. The charter will detail the roles and responsibilities of the DMC members once they have been appointed. The study data will be provided to the Committee members in the form of a data report. Meetings to discuss the data will be held in person or by teleconference, based on the DMC Chair's decision. The meetings will be in two stages: an "open stage" which will involve discussion on general aspects of the trial, and a "closed stage" between the DMC members only. The remit of the DMC will be primarily to assess the safety aspects of the trial.

CONFIDENTIAL Page 95 of 108

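### The DMC toxicity trigger in Protocol 9.1.10 names Grades 3 and 4 only, so read literally one drug-related death does not require DMC review

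*Protocol*

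**What the plan says.** Protocol 9.1.10 (Study Stopping Rules) gives four events after which the DMC reviews the data and makes a recommendation. The investigators, consulting the sponsor, then decide whether to stop enrollment.

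- Trigger 1 (toxicity): "Occurrence of a Grade 4 toxicity or two (2) occurrences of Grade 3 toxicities that are assessed" as definitely, probably or possibly drug-related by the treating investigator.
- Trigger 2 (mortality): "Occurrence of more than 20 percent mortality by day +100". No denominator is given and no cause of death is specified.
- Triggers 3 and 4 concern graft failure above 5% by day +100 and acute Grade II-IV GVHD in at least 5 of the first 10 subjects.

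On grading, 9.1.3 states that the "investigator will use the guidelines outlined in CTCAE v4.03". Table 9-1 lists five grades. Grade 4 is life-threatening, and Grade 5 is a separate line: "Death related to AE".

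The rule just before, 9.1.9 (Stopping Rules for PRO 140), discontinues a subject's treatment for "Grade 3 or higher toxicity which is assessed by the investigator to be definitely, probably or possibly related to the study drug".

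On the adverse event window, 9.1.1 says: "Report initiation for all AEs and SAEs will begin at the time of the first treatment and continue up until the final study visit". The schedule of assessments (Table 4-1) includes adverse events at Follow-up Visit 2, Day 365±14.

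On meetings, section 12 says: "The DMC meetings will take place at least once after the IA". Further time-points are left to the charter, and "the DMC may also decide to schedule a meeting whenever they decide a review of emergent safety data is warranted".

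**The concern.** A rule that compels DMC review after one related life-threatening toxicity should also compel it after one related fatal toxicity. As worded, trigger 1 does not. Grade 5 is neither a Grade 4 event nor a pair of Grade 3 events, and the inclusive wording used in 9.1.9 is absent here.

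If the rule is applied as written, prompt DMC review of a related death while others are still being enrolled and dosed depends on three things: the DMC choosing to meet, the death falling conveniently before the 10-subject interim, or the DMC charter, which is not among these documents. At stake is subject protection in a proof-of-concept study in a new indication. No endpoint, analysis or error rate is affected.

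**Working it through.** The plan states no figure to reproduce here. The check compares the texts and then counts.

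**Step 1. Does a related Grade 5 event meet trigger 1?** The inputs are trigger 1 in 9.1.10 and Table 9-1. The first limb needs a Grade 4 event, and Table 9-1 keeps Grades 4 and 5 apart. The second limb needs two Grade 3 events. A death entered as Grade 5 satisfies neither limb. The protocol extends grades upward in 9.1.9 but not in 9.1.10.

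**Step 2. Does another trigger cover it?** Triggers 3 and 4 count graft failures and GVHD cases, not deaths. Only trigger 2 counts deaths. It needs d/N > 0.20, so the smallest qualifying number of deaths is d = floor(0.2 × N) + 1. Because the protocol gives no denominator, a range of N is shown, up to one arm (30) and the full trial (60):

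| N | Smallest d | d/N | One death fewer |
|---|---|---|---|
| 4 | 1 | 25.0% | 0/4 = 0% |
| 5 | 2 | 40.0% | 1/5 = 20.0%, not enough |
| 9 | 2 | 22.2% | 1/9 = 11.1% |
| 10 | 3 | 30.0% | 2/10 = 20.0%, not enough |
| 20 | 5 | 25.0% | 4/20 = 20.0%, not enough |
| 30 | 7 | 23.3% | 6/30 = 20.0%, not enough |
| 60 | 13 | 21.7% | 12/60 = 20.0%, not enough |

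A single death exceeds 20% only while N is 4 or fewer. By contrast, one related Grade 4 event in 60 subjects (1/60 = 1.7%) compels review under trigger 1. If mortality were judged on all 60 planned subjects, 12 deaths would still not meet trigger 2.

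**Step 3. What about deaths after day 100?** Trigger 2 stops at day +100. Adverse events are assessed up to Day 365, which is 365 − 100 = 265 days later. A related Grade 5 event in that interval meets neither trigger 1 nor trigger 2, however many there are.

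**Step 4. Does anything outside 9.1.10 compel review?**

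- Section 12 lets the DMC meet when it chooses but does not require it to.
- The safety interim (Protocol 8.5, SAP 5) occurs once, after the first 10 subjects complete treatment or withdraw. The DMC then receives AEs and SAEs (SAP 5.1.2).
- Fatal events are SAEs (9.2), and the reporting text in 9.2.1 does not call for a DMC review.
- Protocol 8.5 says the SAP holds the details of the stopping rule, but SAP 5 states none.

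**Step 5. With the wording corrected.** If trigger 1 covered Grade 4 or higher, one related death would compel review at any N and at any time in the adverse event window.

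**The case against.** The strongest reply is that nobody would apply the rule this way. A DMC, medical monitor or investigator would treat a related death as at least Grade 4, and the inclusive wording in 9.1.9 suggests that Grade 4 was meant as a floor. That is probably right, and it makes this a drafting omission, not a deliberate choice.

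Other points also narrow the gap:

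- A fatal toxicity first recorded as Grade 4 would already have met trigger 1. Accompanying related Grade 3 events, graft failure or GVHD could set off a trigger in the same subject.
- The protocol cites transplantation-related mortality as high as 20-30%, so trigger 2 is best read as a check on background mortality. The table above shows how little it can substitute for trigger 1. It does not show that trigger 2 is badly set.
- SAEs go to the IRB, and qualifying events go to FDA and all participating investigators as expedited reports (9.2.1). Those who decide on stopping enrollment would therefore hear of a qualifying death.
- Dosing ends at Day 98±3, so the 265 days are a calendar interval after treatment. They are not a measure of risk.
- The charter may already require review of related deaths.

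These points limit the practical consequence. They do not change the text: an earlier Grade 4 entry or a coinciding graft failure triggers review through that event and not through the death, and none of the other routes seen here makes DMC review mandatory.

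**Conclusion.** The concern holds. Trigger 1 is wrong as written: followed exactly, it compels review after one related life-threatening event but not after one related fatal event. Trigger 2 then needs 3 deaths in 10 subjects, 7 in 30 or 13 in 60 by day +100, and no deaths after that date count.

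The practical effect is modest, because the omission is probably unintended and other safety routes exist.

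The conclusion rests on a literal reading, on the death being recorded as Grade 5 with no other triggering event in the same case, and on what 9.1.10 itself requires. What the DMC charter adds is unknown. The death counts depend on the denominator, which the protocol leaves open.

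**What to change.** Reword trigger 1 in 9.1.10 to cover one toxicity of Grade 4 or higher, explicitly including Grade 5, or two Grade 3 toxicities. Leave the relatedness condition unchanged. Put the same wording in the DMC charter.

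No new data are needed, because fatal adverse events are already reported as SAEs. The cost is one phrase in each document and an ad hoc DMC review after each death judged at least possibly related to study drug.

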# 9.2 SERIOUS ADVERSE EVENTS (SAE)

A SAE is defined as any AE that:

- Results in death
- Is life threatening (the subject is at immediate risk of dying from the AE)
- Requires subject hospitalization or prolongs existing hospitalization
- Results in persistent or significant disability/incapacity
- Is a congenital anomaly/birth defect
- Important medical events that may not result in death, be life-threatening, or require hospitalization may be considered a serious adverse device effect when, based upon appropriate medical judgment, they may jeopardize the subject and may require medical or surgical intervention to prevent one of the outcomes listed in this definition.

# 9.2.1 Reporting of SAE

The Investigator is required to report all SAEs that occur during the time period specified in section 9.1.1. Once the Investigator becomes aware of an SAE, he/she must report the SAE to

The Medical Monitor may request additional supporting documentation as it becomes available, such as lab reports, ECG reports, discharge summary, hospital notes, etc.

The Investigator is also responsible for reporting all SAEs to the appropriate Institutional Review Board (IRB) in accordance with local laws and regulations. The Investigator is responsible for maintaining documentation in the study file that indicates the IRB has been properly notified.

CONFIDENTIAL Page 90 of 108

Under 21 CFR 312.32(c), the sponsor is required to notify FDA and all participating investigators in an IND safety report (i.e., 7- or 15-day expedited report) of potentially serious risks from clinical trials or any other source as soon as possible, but no later than 15 calendar days after the sponsor receives the safety information and determines that the information qualifies for reporting. Participating investigators include all investigators to whom the sponsor is providing drug under any of its INDs or under any investigator's IND (21 CFR 312.32(c)(1)).

# 9.2.2 SAE Follow-Up

All subjects experiencing an SAE, including the discontinued subjects, must be closely followed until sufficient information is obtained to indicate a return to normal status or until the event stabilizes at a level acceptable to the investigator (i.e., recovery, return to baseline status, no further improvement expected, or death).

For each SAE indicated as an unresolved event on the initial report, regardless of whether the subject completed the study or withdrew, the site should submit a follow-up report with updated information.

# 9.2.3 Pregnancy

If a pregnancy occurs in a subject or partner of a male subject during the study, it must also be reported to CytoDyn, Inc. Any pregnant subject must be followed up by the Investigator or designee until the child is born. Any complication experienced through the end of the pregnancy should be considered as an adverse event (AE), and should be recorded, and if it meets the seriousness criteria, it must be reported CytoDyn, Inc/designated CRO promptly.

CONFIDENTIAL Page 91 of 108

### 10 DIRECT ACCESS TO SOURCE DATA/DOCUMENTATION

Subjects will be identified on eCRFs by a unique subject identification number and on source documents by name and date of birth. No personal identifier will be used in any publication or communication used to support this research study. The subject identification number will be used if it becomes necessary to identify data specific to a single subject.

The monitors, auditors, personnel authorized by the Sponsor, the local IRB, and the FDA are eligible to review medical and research records related to this study as a part of their responsibility to protect human subjects in clinical research and will be given direct access to source data and documentation (e.g., medical charts/records, printouts etc.) for source data verification, provided that subject confidentiality is maintained in accordance with local requirements. Access to electronic medical records may be governed by institution policy and each site will be required to ensure access while remaining compliant with institutional requirements.

CONFIDENTIAL Page 92 of 108

# 11 QUALITY CONTROL AND QUALITY ASSURANCE

### 11.1 MONITORING REQUIREMENTS

In an effort to fulfill the obligations outlined in 21 Code of Federal Regulations (CFR) Part 312 and ICH guidelines which requires the Sponsor to maintain current personal knowledge of the progress of a study, the Sponsor's designated monitor will visit the center(s) during the study as well as maintain frequent telephone and written communication. The Investigator will permit the Sponsor to monitor the study as frequently as is deemed necessary and provide access to medical records to ensure that data are being recorded adequately, that data are verifiable and that protocol adherence is satisfactory.

The Investigator will permit representatives of the Sponsor and/or designated CRO to inspect all eCRFs and corresponding study subject original medical records (source documents) at regular intervals throughout the study. Subject original medical records and other relevant data must be available to support all data recorded in the eCRF. In addition to the original medical records, these data may include but are not limited to, study, laboratory and diagnostic reports, ulcer images, quality of life questionnaire, etc.

Site inspections serve to verify strict adherence to the protocol and the accuracy of the data being entered on the case report forms, in accordance with federal regulations. A Monitoring Log will be maintained at each study site which the monitor will sign, date and state the type of visit.

The Investigator should be aware that the study site and subject records may be inspected by the Sponsor and or representatives of the designated CRO, FDA or other regional regulatory authority.

# 11.2 ACCEPTABILITY OF CASE REPORT FORMS (CRFs)

Electronic CRFs must be completed for each subject who has signed an informed consent form. For subjects who are screen failures, this would be limited to the screen failure eCRF page. All source documents and eCRFs will be completed as soon as possible after the subject's visit. Corrections to data on the eCRFs will be documented. The Investigator will review eCRFs to indicate that, to his/her knowledge, they are complete and accurate. Electronic CRFs will be reviewed by the Sponsor's or designated CRO's monitor, who will make a decision as to their acceptability.

# 11.3 MODIFICATION OF PROTOCOL

The Investigator will not modify or alter this protocol without first obtaining the concurrence of the Sponsor. Approval by the Investigator's IRB must also be obtained prior to implementation of the change, with two exceptions:

CONFIDENTIAL Page 93 of 108

[figure not shown]
- 1. When necessary to eliminate apparent immediate hazard to the subject; or
- 2. When the modification does not involve the subject's participation in the trial.

An amendment may also require modification of the informed consent form. The Investigator will provide an approval letter for the amendment and revised informed consent form, if applicable, to the Sponsor. An amendment must be in writing and it must be dated by both the Sponsor and the Investigator. If necessary, the Sponsor will submit protocol amendments to FDA and other appropriate regulatory authorities and notify other Investigators using this protocol.

# 11.4 REPORTING PROTOCOL DEVIATIONS

The Investigator is obligated to follow the protocol without departure from the requirements written in the protocol. If the Investigator deviates from the protocol requirements, the Sponsor will make the determination as to whether the subject will continue in the study. The Sponsor also has the right to discontinue the subject for protocol violations. The IRB may also have to be contacted if safety to the subject or if the scientific soundness of the study is involved. All protocol deviations must be documented in the eCRFs.

CONFIDENTIAL Page 94 of 108

[figure not shown]

# 12 DATA MONITORING COMMITTEE (DMC)

A Data Monitoring Committee (DMC), independent of the study operations will be established to consider safety data generated during the study and to make recommendations about IA data. The details of the DMC responsibilities will be included in the DMC charter. The DMC charter will be developed and operated in adherence to the current FDA guidance on DSMC (Establishment and Operation of Clinical Trial Data Safety Monitoring Committees [March 2006]). The DMC meetings will take place at least once after the IA, and at other time-points as determined by the DMC charter, if necessary. In addition to the pre-specified time-points, the DMC may also decide to schedule a meeting whenever they decide a review of emergent safety data is warranted. The charter will detail the roles and responsibilities of the DMC members once they have been appointed. The study data will be provided to the Committee members in the form of a data report. Meetings to discuss the data will be held in person or by teleconference, based on the DMC Chair's decision. The meetings will be in two stages: an "open stage" which will involve discussion on general aspects of the trial, and a "closed stage" between the DMC members only. The remit of the DMC will be primarily to assess the safety aspects of the trial.

CONFIDENTIAL Page 95 of 108

### 13 ETHICS AND REGULATORY REQUIREMENTS

This study is to be conducted in accordance with the specifications of this protocol and in accordance with principles consistent with Declaration of Helsinki, GCP, 21 CFR Part 312, ICH E6, HIPAA regulations in 45 CFR Part 164 (US only), and the Belmont Principles of respect for persons, beneficence, and justice. Procedures for selection of donors and stem cell dose will follow FDA requirements for Blood Products (21 CFR 640) and Human Cellular and Tissue Based Products (21 CFR 1271). No protocol changes will be implemented without the prior review and approval of the IRB, except when the modification does not involve the subject's participation in the trial or where it may be necessary to eliminate an immediate hazard to a research subject. In the latter case, the change will be reported to the IRB as soon as possible, according to IRB regulations.

Additionally, all study products used in this study are manufactured, handled and stored in accordance with applicable GMP and the products provided for this study will be used only in accordance with this protocol.

